and flow cytometry analysis. 4. Laboratory assessments: • Hematology to include platelet count, hemoglobin, hematocrit, white blood cells (WBC) and WBC differential (including: neutrophils, eosinophils, basophils, lymphocytes and monocytes), INR, PT, PTT, and reticulocyte count. • Clinical chemistries including BUN/urea, creatinine, sodium, potassium, alkaline phosphatase, alanine aminotransferase (ALT), aspartate aminotransferase (AST), total bilirubin, total bilirubin, albumin. • Urine or serum pregnancy test for females of childbearing potential will be performed at Screening or on Day 1, prior to first dose of study medication. 5. Review and record any blood and blood supportive care products for the prior 8 weeks. Treatment will be administered on an outpatient basis. Reported adverse events and potential Treatment risks are described in Section 11. Appropriate dose modifications for ruxolitinib are described in nlan Section 10. No investigational or commercial agents or therapies other than those described below may be administered with the intent to treat the patient's CMML. Ruxolitinib will be supplied by INCYTE as 5mg tablets containing ruxolitinib. Ruxolitinib will be self-administered as a twice-daily oral dose for a continuous treatment cycle. Ruxolitinib tablets will be taken approximately 12 hours apart (morning and night). Subjects will not take the morning dose of ruxolitinib at the first regularly scheduled visit. Drug will be administered in the clinic in order to obtain adequate biomarker assessment. On all other days corresponding to study visits, subjects will take the morning dose of study drug prior to the visit, and will note on the subject reminder card the time that medications were taken. Subjects will also be instructed to take ruxolitinib without respect to food, as previous data demonstrate no change in drug kinetics or absorption. The first patient will be given 10 mg/day divided in equal BID doses. Dose escalation guidelines are detailed below in section 10. In phase II of the study, a maximum of 29 subjects will be treated at the MTD identified in phase I. See study calendar for assessment on study. All subjects enrolled in phase 1 will start treatment on the assigned dose per cohort based on the Dose delay/modif dose escalation algorithm provided. Dose delays/modifications will not be allowed in phase 1 as it -ications will interfere with the primary endpoint of this study. Dose delays/modifications are allowed for those subjects enrolled in phase II as described in section 6. Definition Dose-limiting toxicity (DLT) is defined as any grade 4 hematologic toxicity and any grade 3 or of Dosegreater non-hematologic toxicity except nausea that is controlled by antiemetic therapy based on Limiting the NCI Common Terminology Criteria for Adverse Events (CTCAE) version 4.0. Grade 3 metabolic/electrolyte abnormalities that are not clinically significant, and are adequately Toxicity controlled within 72 hours are not to be considered a DLT. To discern disease specific versus drug specific myelosuppression, Grade 4 thrombocytopenia will be defined as a decrease of > 50% of baseline and a level of < 25,000/uL. Grade 4 neutropenia will be defined as a decrease of $\ge 50\%$ of baseline and a level of <500/uL. Subjects will be evaluated for DLTs during the first and second cycles of therapy, i.e. 8 weeks for purpose of deciding the dose for next cohort (see dose escalation schema) but DLTs will continue to be evaluated and reported through all cycles on **Duration of** Subjects will be treated for a total of 16 weeks. For subjects responding at week 16, treatment may continue until one of the following criteria applies: **Therapy** Dose-limiting toxicity is reached, Inter-current illness that prevents further administration of treatment, Unacceptable adverse event(s), Patient decides to withdraw from the study, or General or specific changes in the patient's condition render the patient unacceptable for further treatment in the judgment of the investigator. Evidence of disease progression by the IWG 2006 criteria. Subjects who wish not to continue treatment will complete their end of study visit at week 16.

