
Subjects who were not enrolled in the MTD cohort can increase to the MTD after week 16 if the participant still meets the eligibility criteria. Responding patients will be able to continue treatment until marketing approval of ruxolitinib for CMML. **Duration of** Subjects will be followed as per calendar on treatment for 17 weeks. After 17 weeks, subjects who continue on study will be followed monthly. Off study data on AML transformation and Follow-Up overall survival will be updated every 6 months or until death, whichever occurs first. Subjects removed from the study for unacceptable adverse events will be followed until resolution or stabilization of the adverse event. Criteria for Removal from Study Study drug treatment can continue for subjects receiving clinical benefit, unless; one or more withdrawal criteria are met, or at the subject's discretion, or if the study is terminated, or until the marketing approval for CMML *Subject Completion A subject will be considered to have completed the study if the subject meets at least 1 of the following criteria: - The subject has completed 16 weeks of treatment with study medication with no improvement. - The subject died during the study. - The subject withdrew from study including subjects who experience a DLT. - The subject experienced an AE that lead to withdrawal from the study. *Subject Withdrawal from Study A subject may voluntarily withdraw from study medication or withdraw consent from the study at any time. The investigator may also, at his or her discretion, discontinue a subject from participating in the study at any time. The investigator will record the date and the reason for subject withdrawal from the study. *Subject Withdrawal from Study Medication If the subject is permanently withdrawn from treatment with study medication, but does not withdraw consent, the investigator must make every effort to have the subject complete all withdrawal assessments at the time of withdrawal, and complete all scheduled follow-up visits. Treatment with study medication must be discontinued if (Withdrawal Criteria): • No clinical benefit has been attained after 16 weeks of treatment. • Evidence of Disease progression according to IWG 2006 criteria. a subject experiences a DLT. • a subject becomes pregnant. • a subject is significantly non-compliant with the requirements of the protocol; • a subject has an adverse experience that would, in the investigator's judgment, make continued participation in the study an unacceptable risk See calendar page 36 Follow up on study **Statistics Study Design:** This study will use a dose escalation, "rolling 6" design in Phase 1. Subjects will be allocated to starting doses of 10 mg/d to 40mg/d (divided in two equal doses) escalated by 10 mg/day for each cohort according to the predetermined algorithm outlined below in Table 1 (section 6.4). Each cohort will include 6 subjects. After testing the treatment dose on 10 patients in the first stage, the trial will be terminated if 1 or fewer desired respond. If the trial goes on to the second stage, a total of 29 patients will be studied. If the total number responding is less than or equal to 5, the drug is rejected. *Sample Size/Accrual Rate

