6 TREATMENT PLAN

6.1 Ruxolitinib administration

Subjects will not take the morning dose of ruxolitinib at the first regularly scheduled visit. Drug will be administered in the clinic in order to obtain adequate biomarker assessment. On all other days corresponding to study visits, subjects will take the morning dose of study drug prior to the visit, and will note on the subject reminder card the time that medications were taken. Reported adverse events and potential risks are described in Section 11. Appropriate dose modifications for ruxolitinib are described in Section 10. No investigational or commercial agents or therapies other than those described below may be administered with the intent to treat the patient's CMML.

6.1.1 Ruxolitinib will be supplied by INCYTE as tablets that will be self-administered BID orally, with or without food approximately 12 hours apart (morning and night).

6.1.2 The dosage strength is 5 mg/tablet Ruxolitinib phosphate (free base equivalent). Administration instructions will be provided at Study Visits. The administration instructions will state that medication is "For Investigational Use Only". Ruxolitinib 5 mg tablets are packaged as 60 count in high-density polyethylene (HDPE) bottles. The bottles will include labeling "New Drug - Limited by Federal (USA) Law to Investigational Use. The bottles of tablets should be stored at room temperature, 15°C to 30°C (59°F to 86°F). Dose escalation guidelines are detailed below in section 6.5. In phase II of the study, a maximum of 29 subjects will be treated at the MTD identified in phase I.

6.2 **Definition of Dose-Limiting Toxicity**

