Dose-limiting toxicity (DLT) is defined as any grade 4 hematologic toxicity and any grade 3 or greater non-hematologic toxicity except nausea that is controlled by antiemetic therapy based on the NCI Common Terminology Criteria for Adverse Events (CTCAE) version 4.0. Criteria for Grade 3 renal toxicity are consistent with prescribing information with respect to renal impairment and safe use of ruxolitinib. Grade 3 metabolic/electrolyte abnormalities that are not clinically significant, and are adequately controlled within 72 hours are not to be considered a DLT. To discern disease specific versus drug specific myelosuppression, Grade 4 thrombocytopenia will be defined as a decrease of $\geq 50\%$ of baseline and a level of $\leq 25,000/\text{uL}$. Grade 4 neutropenia will be defined as a decrease of $\geq 50\%$ of baseline and a level of < 500/uL. Previous clinical trials testing ruxolitinib reported a hematologic nadir of 8 weeks. As such, DLTs during the first and second cycle of therapy, i.e. 8 weeks, will be used for the purpose of deciding the dose for next cohort (see dose escalation schema) but DLTs will continue to be evaluated and reported through all cycles on study. Management and dose modifications associated with the above adverse events are outlined in Section 11.

6.2.1 Dose escalation will proceed according to the following scheme:

Dose Escalation Schedu	ıle

Dose Level	Dose of Ruxolitinib (per day given in equal BID
	doses)
Level 1	10 mg
Level 2	20 mg
Level 3	30 mg
Level 4	40 mg

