9.3 Subject Withdrawal from Study Medication

If the subject is permanently withdrawn from treatment with study medication, but does not withdraw consent, the investigator must make every effort to have the subject complete all withdrawal assessments at the time of withdrawal, and complete all scheduled follow-up visits. Treatment with study medication must be discontinued if:

- The subject withdraws consent.
- Further participation would be injurious to the subject's health or well-being in the Investigator's medical judgment.

- The study is terminated.
- Marketing approval of CMML
- The subject becomes pregnant
- The subjects exhibits leukemic transformation (as evidenced by bone marrow blast counts of at least 20%, or peripheral blast counts of at least 20% lasting at least 8 weeks.
- No clinical benefit has been attained after 16 weeks of treatment.
- Evidence of Disease progression according to IWG 2006 criteria.
- a subject experiences a DLT.
- a subject is significantly non-compliant with the requirements of the protocol.
- a subject has an adverse experience that would, in the investigator's judgment, make continued participation in the study an unacceptable risk.

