10 DOSING DELAYS/MODIFICATIONS

All subjects enrolled in the phase 1 portion will start treatment on the assigned dose per cohort based on the dose escalation algorithm provided. No dose delays or modifications are allowed during this period. All subjects enrolled in the phase 2 portion may have the following dose delays/modifications once the MTD has been defined.

Ruxolitinib may be held by the Investigator at any time if there is concern about subject safety. Dosing must be halted immediately if either of the following occurs:

- Platelet counts fall below 10,000/μL and/or a life-threatening bleeding event
- Febrile neutropenia

Dosing may be reinstated following dose interruption using the re-start schema detailed in below.

10.1 Dose Adjustments.

In order to provide sufficient data to make the dose adjustment decisions, it is recommended that hematology parameters be obtained weekly and at least two times weekly for platelet count $< 25,000/\mu L$ or ANC $< 500/\mu L$. In the event that any subject permanently discontinues the study drug, regardless of reason, reasonable efforts should be made to have the subject return for an early termination visit. If the drug discontinuation is being contemplated for a reason other than low platelet count or

low ANC, the use of a tapering strategy should be considered (see below). The date the subject discontinued the study drug and the specific reason for discontinuation will be recorded in the eCRF; eg, reasons such as discontinued due to inadequate efficacy or withdrawn due to adverse event. This information will be used to summarize the reasons for study discontinuation. Efforts will be made to follow subjects who discontinue from the study in order to determine overall survival and leukemia free survival. Investigators will contact subjects every 6 months to determine if subjects have undergone leukemic transformation, or death, and for the latter, the cause of death.

10.2 Dose Adjustments in Ruxolitinib Tablets for Safety.

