Dose adjustments apply to the phase 2 portion of this study. There are no dose adjustments allowed during phase 1. Dosing must be held if platelet counts decline below 10,000/μL or if a life-threatening bleed occurs with a platelet count below 20,000/μL. Doses must be decreased for platelet count values that decline greater than 50% of baseline and are greater than 25,000/μL to 75% of the defined MTD. Doses must be decreased for platelet count values that decline greater than 50% of baseline and are below 25,000/μL to 50% of the defined MTD. The dosing scheduled should be maintained at BID dosing to assure appropriate pharmacokinetics. Dose reductions should be executed by decreasing the individual dose and not the frequency of administration. In order to provide sufficient data to make the dose adjustment decisions, it is recommended that hematology parameters be obtained as defined in section 10.1. Dosing may be restarted or increased following recovery of platelet counts to acceptable levels. The following is the recommended dose restart/increase strategy:

In subjects whom drug was held, ruxolitinib may be restarted at 50% of the MTD after platelet count has improved to pre-ruxolitinib baseline levels and/or febrile neutropenia has resolved for at least 2 weeks. In subjects whom drug dose was decreased, ruxolitinib may be increased to the previous dose (MTD) after platelet count has improved to pre-ruxolitinib baseline levels and/or febrile neutropenia has resolved for at least 2 weeks. If criteria is met for discontinuation/dose modification then ruxolitinib must be discontinued with no potential for restart. The objective for

restarting or escalating after a reduction for safety is to find the highest safe dose of ruxolitinib for each subject, with increases in dose generally not more than in increments of 5 mg BID and not more often than every 2 weeks. Subjects who were not enrolled in the MTD cohort can increase to the MTD after week 17 if the participant still meets the eligibility criteria. Non hematological toxicity dose adjustment criteria

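### A phase 2 platelet DLT must stop treatment under 9.3 and the synopsis but only halve the dose under 10.2; Section 10 applies to phase 2, yet nothing exempts phase 2 from the DLT stop

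*Combined protocol and SAP*

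**What the plan says.** **What counts as a DLT.** Any grade 4 hematologic toxicity is a DLT. In the synopsis, "Grade 4 thrombocytopenia will be defined as a decrease of > 50% of baseline and a level of < 25,000/uL". Section 6.2 gives the same definition with inclusive limits (a fall of at least 50%, and 25,000/uL or lower). Section 6.2 uses the first 8 weeks to choose the next cohort's dose, but adds that "DLTs will continue to be evaluated and reported through all cycles on study".

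**What follows a DLT.** The synopsis introduces its list of mandatory stops with "Treatment with study medication must be discontinued if (Withdrawal Criteria". Both that list and the one in 9.3 include the case where "a subject experiences a DLT". Neither list is limited to phase 1.

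**What 10.2 requires.** "Doses must be decreased for platelet count values that decline greater than 50% of baseline and are below" 25,000/uL; the new dose is 50% of the MTD. Once platelets return to the pre-treatment level, the dose may go back up to the MTD. Below 10,000/uL the drug is held, and after recovery it may be restarted at 50% of the MTD.

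**Scope.** Section 10 states: "All subjects enrolled in the phase 2 portion may have the following dose delays/modifications once the MTD has been defined". Section 10.2 opens by saying that its adjustments are for phase 2. Section 6.1 points the same way: "Appropriate dose modifications for ruxolitinib are described in Section 10". Two other pointers go elsewhere. Section 6.2 sends the reader to Section 11, which covers adverse event reporting, and the synopsis row on dose delays and modifications sends the reader to section 6.

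**The concern.** A phase 2 patient whose platelets fall by more than half to below 25,000/uL comes under two mandatory instructions that cannot both be followed. One ends treatment. The other continues it at half the MTD and may restore the full dose. For a patient who falls below 10,000/uL, the question is whether the drug may be given again at all. The answer depends on which page the site reads. The rule for severe thrombocytopenia on a myelosuppressive drug should not be left to that. Different choices would also mean that patients with the same event are treated differently within one single-arm cohort.

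**Working it through.** The plan gives no figure to reproduce here. The check is whether the events that trigger 10.2 are also DLTs, and then whether any passage separates the two rules.

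**Inputs.** DLT platelet limits: synopsis and 6.2. Reduction and hold triggers: 10.2. Entry floor: 4.2.1.1 excludes counts under 35,000/uL. Assumption: the baseline used in 10.2 is close to the count at eligibility, so at least 35,000/uL.

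**Step 1: the reduction rule.** The 10.2 trigger is a fall of more than 50% and a count below 25,000/uL. That is the synopsis DLT definition, and it also satisfies the inclusive limits in 6.2. Every event that calls for 50% of the MTD is therefore a DLT under both wordings.

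The range in which 10.2 says reduce and 9.3 says stop runs from 10,000/uL (below which 10.2 says hold) up to the smaller of 25,000 and 0.5 × baseline:

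| Baseline (/uL) | 0.5 × baseline | Range in conflict (/uL) |
|---|---|---|
| 35,000 | 17,500 | 10,000 to below 17,500 |
| 40,000 | 20,000 | 10,000 to below 20,000 |
| 45,000 | 22,500 | 10,000 to below 22,500 |
| 50,000 or more | 25,000 or more | 10,000 to below 25,000 |

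The milder step in 10.2, to 75% of the MTD, applies above 25,000/uL. That count does not meet the platelet DLT definition, so that step is not in conflict.

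**Step 2: the hold-and-restart rule.** At the lowest admissible baseline, a count of 10,000/uL is a fall of (35,000 − 10,000) / 35,000 = 71.4%. A lower count or a higher baseline makes the fall larger. Any count below 10,000/uL is therefore also a DLT, and 9.3 rules out the restart that 10.2 permits.

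**Step 3: is there a passage that decides?**
- Section 10 and 10.2 give their scope as phase 2. They do not mention 9.3.
- Section 9.3 and the synopsis list have no phase limit. The same lists contain general stops such as pregnancy and progression.
- Section 6.1 points to Section 10 without giving it precedence. The pointers in 6.2 and the synopsis modification row do not reach the dose rules.
- One sentence in 10.2 says that meeting criteria for discontinuation or dose modification ends treatment for good. It might mean recurrence after a restart, as 10.4 provides for hepatic impairment, or it might point back to 9.3. Read literally, it cancels the restart and re-escalation rules just before it. It settles nothing.

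**The case against.** The best defense is that the specific rule governs the general one. Section 10 is the detailed phase 2 dosing section, it says so, and 6.1 sends the reader there. A site could reasonably conclude that 9.3 was written with phase 1 in mind. The part about intent stands. If 9.3 always prevailed, the reduction to 50% of the MTD could never be used, and nobody writes a rule for that purpose. But intent has to be inferred. Section 9.3 is equally mandatory, and DLT-ends-treatment wording recurs in 7.1, 9.1.3 and the continuation phase.

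A second defense favors the other side: the no-restart sentence in 10.2 may refer to 9.3, so stopping wins. That reading is possible, but no better supported than recurrence.

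It is also fair to object that choosing 10.2 over 9.3 relaxes a safety stop, which is a clinical decision. That stands, and it is why the fix asks the sponsor to confirm re-dosing.

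A reader might infer more than the documents support:
- That the plan fails to say Section 10 applies to phase 2. It does say so; only the exemption from the DLT stop is missing.
- That every hold in 10.2 conflicts with 9.3. The hold for a life-threatening bleed below 20,000/uL need not meet the platelet DLT: 19,000 from 35,000 is a fall of (35,000 − 19,000) / 35,000 = 45.7%.
- That the response rate is biased. The documents give no event rate, and some responders with this event would stop anyway, because Appendix B counts a 50% loss from the best platelet level as progression. Neither direction nor size can be stated.

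**Conclusion.** The conflict is real and is an error in the text as written. For a phase 2 platelet fall of more than 50% to below 25,000/uL, the overlap between the 10.2 trigger and the DLT definition is complete, and the two required actions are incompatible. The restart after a count below 10,000/uL conflicts in the same way, on the assumption that baseline is at or above the 35,000/uL eligibility floor. The rules cover everyone in phase 2, up to 29 patients. That is the number exposed to the ambiguity, not the number who will have the event, which cannot be computed. Sample size and error rates are unaffected. The point should be corrected because it governs a safety action.

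**What to change.** - In 9.3 and the synopsis withdrawal criteria, keep the DLT stop in both phases but except phase 2 platelet DLTs managed under 10.2. Do not confine the stop to phase 1: it must stay for non-hematologic DLTs, for which 10.2 gives no rule (its text ends at a title with nothing after it).
- Have the sponsor confirm that re-dosing after a count below 10,000/uL is intended. If it is not, delete that restart rule from 10.2 instead.
- Reword the no-restart sentence in 10.2 to name the event it covers, for example recurrence after restart or reduction.
- State that the progression stop still applies to patients managed under 10.2.
- Match the DLT wording in 7.1, 9.1.3 and both statements of the continuation phase in Section 13.
- Point 6.2 and the synopsis dose-modification row to Section 10.

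The cost is a wording amendment and one clinical confirmation by the sponsor. It needs no extra patients, visits or procedures.

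### In phase 2, Section 9.3 orders ruxolitinib stopped for a platelet fall that Section 10.2 orders treated at half the MTD

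*Combined protocol and SAP*

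**What the plan says.** **The stop rule.** Section 9.3 reads "Treatment with study medication must be discontinued if" any of a list of criteria applies. One of them is that "a subject experiences a DLT". The synopsis withdrawal criteria repeat this. Neither place limits it to phase 1.

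**The DLT definition.** Under Section 6.2 and the synopsis, any grade 4 hematologic toxicity is a DLT. For platelets, the synopsis asks for a fall of more than 50% from baseline to below 25,000/µL; 6.2 asks for at least 50%, to 25,000/µL or lower. DLTs in the first 8 weeks drive escalation, but 6.2 keeps assessing them in all later cycles. It then says that management and dose modification of these events are given in Section 11. That section covers adverse event reporting; the dose rules are in Section 10.

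**The dose rules.** Section 10.2 applies to phase 2 only. "Doses must be decreased for platelet count values that decline greater than 50% of baseline and are below" 25,000/µL, to half the MTD. After the same relative fall with a count above 25,000/µL, the dose goes "to 75% of the defined MTD". Below 10,000/µL the drug is held, and then "ruxolitinib may be restarted at 50% of the MTD after platelet count has improved to pre-ruxolitinib baseline levels". On how to reduce: "Dose reductions should be executed by decreasing the individual dose and not the frequency of administration". The section also states: "If criteria is met for discontinuation/dose modification then ruxolitinib must be discontinued with no potential for restart".

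**The concern.** Both instructions are mandatory, both cover a phase 2 patient whose platelets have more than halved to below 25,000/µL, and no sentence says which prevails. One investigator may stop the drug for good under 9.3, and another may continue at half dose under 10.2. Each would breach a requirement of the protocol. This is a safety decision at very low counts, and patients with the same event could be handled differently.

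There is a smaller practical question. The reductions are percentages of the MTD, the only strength is a 5 mg tablet, and no rule covers rounding, splitting or unequal morning and evening doses.

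**Working it through.** The plan states no figure for this point, so there is none to reproduce. The check compares the rules and then tests the doses.

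**Step 1. Is the 10.2 event always a DLT?** Let *b* be baseline and *c* the on-study count.

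| Rule | Condition | Action |
|---|---|---|
| 10.2, lower band | (b − c)/b > 0.50 and c < 25,000 | Reduce to 50% of MTD |
| DLT, synopsis | (b − c)/b > 0.50 and c < 25,000 | Stop (9.3, synopsis) |
| DLT, 6.2 | (b − c)/b ≥ 0.50 and c ≤ 25,000 | Stop (9.3, synopsis) |

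The first condition equals the second and lies inside the third. A grid of baselines from 35,000 to 400,000/µL gave 7,299 points in the 10.2 lower band, and all of them met both DLT wordings.

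**Step 2. Is a hold below 10,000/µL also a DLT?** Section 4.2.1.1 excludes counts under 35,000/µL. From that floor the fall is at least 1 − 10,000/35,000 = 71.4%, and the count is under 25,000/µL. So it is a DLT for every baseline at or above the floor. Section 9.3 requires a stop, whereas 10.2 permits a restart.

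**Step 3. Does the no-restart sentence in 10.2 settle it?** Three readings are possible.
- Literal: any criterion for dose modification means a permanent stop. This cancels 10.2's own reductions and restarts.
- A criterion in 9.3 has been met: the 50% platelet step then never applies.
- A repeat event: the first event still falls under both 9.3 and 10.2.

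**Step 4. How often?** The documents give no platelet DLT rate for phase 2. The MTD definition (DLTs in under 33% of subjects) does allow DLTs at the phase 2 dose. Purely as an assumption, take a rate *p* of 5%, 10% or 15%. Among 29 patients the expected number is 29p = 1.5, 2.9 or 4.4, and the chance of at least one, 1 − (1 − p)^29, is 77%, 95% or 99%. If the trial stops after 10 patients, 1 − (1 − p)^10 gives 40%, 65% or 80%.

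**Step 5. Can the reduced doses be given?** Assume whole 5 mg tablets and allow unequal morning and evening doses.

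| MTD | 75% per day | Given as | 50% per day | Given as |
|---|---|---|---|---|
| 5 mg BID | 7.5 mg | not possible | 5 mg | 5 mg once daily only |
| 10 mg BID | 15 mg | 10 + 5 mg | 10 mg | 5 + 5 mg |
| 15 mg BID | 22.5 mg | not possible | 15 mg | 10 + 5 mg |
| 20 mg BID | 30 mg | 15 + 15 mg | 20 mg | 10 + 10 mg |

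At 15 mg BID the nearest options to 75% are 10 mg BID (20/30 = 67%) and 15 + 10 mg (25/30 = 83%).

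**The case against.** The best defense is that the specific phase 2 rule should be read over the general list. Section 6.2, directly after defining DLTs, expects these events to be managed with dose modifications, and Section 10 supplies them once the MTD is known. This stands in part. It shows which rule was probably intended and so guides the fix. It does not remove the conflict: 9.3 and the synopsis still require a stop, no precedence is stated, and the 6.2 cross-reference points to the wrong section.

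A second defense is that only drug-related DLTs count, as the MTD endpoint in 3.1.1 says. But 6.2 uses the platelet thresholds themselves to separate drug effect from disease, so attribution is not a clear way out.

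A reader might also infer that the protocol orders a stop after a DLT in many places. It does not. Section 7.1, its synopsis copy and the continuation text in Section 13 limit how long responders may go on after week 16, and 9.1.3 defines study completion. The mandatory stop is in 9.3 and the synopsis withdrawal criteria only.

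On tablets, a reader might conclude that 3 of the 8 combinations of MTD and reduction step are impossible, or 5 of 8 if the two daily doses must be equal. Neither count is firm. The documents do not address splitting, and half tablets with unequal doses would reach all eight daily totals. Section 10.2 words its BID instruction as a recommendation, 10.3 already lists 5 mg once daily, and no text requires reduced doses to be equal.

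**Conclusion.** The conflict between 9.3 (with the synopsis) and 10.2 is real and should be fixed. It covers every phase 2 platelet fall of more than 50% to below 25,000/µL, and the restart after any hold below 10,000/µL. The second part assumes that baseline is at or above the entry floor. The number of patients is unknown; the rates in Step 4 are assumptions with no anchor in the documents and carry no weight in this conclusion.

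A reader might infer that the efficacy result is compromised. The documents do not support that. The first analysis in 15.5 includes all treated subjects whatever their treatment duration. Only the second, evaluable-subject analysis requires 8 weeks of therapy, so the choice of rule matters there only for a patient stopped before week 8. The sample size and error rates in 15.2 do not depend on these rules.

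The tablet point is secondary. It holds for whole tablets and arises only if the MTD is 5 or 15 mg BID. At 5 mg BID, the 50% dose is available only by going against 10.2's advice to keep the frequency.

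**What to change.** 1. In 9.3 and the synopsis withdrawal criteria, limit the DLT stop to phase 1 and to phase 2 DLTs that Section 10 does not manage. Make matching edits in 7.1, 9.1.3, Section 13 and their synopsis copies. This fits 6.2 and 10.2's stated aim of finding each subject's highest safe dose. Letting 9.3 govern and deleting the 50% platelet step and the restart after such holds would also be consistent, but it abandons that aim.
2. Reword the no-restart sentence in 10.2 as a second-occurrence rule, as 10.4 does for hepatic impairment.
3. Correct the 6.2 cross-reference from Section 11 to Section 10.
4. Add a whole-tablet table to 10.2, rounding down where the exact dose cannot be made, for the 75% and then the 50% step:
   - MTD 20 mg BID: 15 mg BID, then 10 mg BID.
   - MTD 15 mg BID: 10 mg BID, then 10 + 5 mg.
   - MTD 10 mg BID: 10 + 5 mg, then 5 mg BID.
   - MTD 5 mg BID: 5 mg once daily or a hold, as a stated exception.

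The cost is one amendment, with no extra patients, visits or tablet strengths. Some patients with grade 4 thrombocytopenia would stay on half dose, as 10.2 already intends. The 75% step at 15 mg BID becomes 67%, and patients given unequal doses need clear instructions.
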